## Department & Unaffiliated Personnel

### Department

What Department does the PI belong to?

Psychiatry

Within the department, what Center or group are you affiliated with, if any?  
Opioid Research Laboratory

### Unaffiliated Personnel

List investigators, if any, who will be participating in this protocol but are not affiliated with New York

---

State Psychiatric Institute or Columbia University. Provide: Full Name, Degrees and Affiliation.  
None

## Procedures

**To create the protocol summary form, first indicate if this research will include any of the following procedures**

- Administration of Substance of Abuse
- Collection of Biological Specimens
- Internet-based Data Collection or Transmission
- Medication Trial
- Psychiatric Assessment
- Use of Investigational Drug or Device

## Population

**Indicate which of the following populations will be included in this research**

- Medically and Psychiatrically Healthy Subjects
- Adults over 50

## Research Support/Funding

Will an existing internal account be used to support the project?

No

Is the project externally funded or is external funding planned?

Yes

Select the number of external sources of funding that will be applicable to this study

## Funding Source #1

Is the PI of the grant/contract the same as the PI of the IRB protocol?

Yes

Select one of the following

The grant/contract is currently funded

Source of Funding

Federal

Institute/Agency

National Institute on Drug Abuse

Grant Name

The Ability of Inhaled Dronabinol to Reduce the Severity of Naloxone-Precipitated Withdrawal.

Grant Number

R21 DA049076-01A1

Select one of the following

Single Site  
Business Office  
RFMH

Does the grant/contract involve a subcontract?

No

## Study Location

Indicate if the research is/will be conducted at any of the following

**NYSPI**

This protocol describes research conducted by the PI at other facilities/locations

No

## Lay Summary of Proposed Research

### Lay Summary of Proposed Research

To address the opioid epidemic, there has been an increased focus on the development of novel medications to treat opioid use disorder (OUD). However, a pharmacological approach more specific to overdose harm reduction (i.e., minimizing the harmful effect of drugs among active users) may be to increase the tolerability of the overdose reversal agent, naloxone (NLX). In emergency settings, NLX administration (in suspected cases of opioid overdose) often results in violent patient behavior, as individuals who are opioid dependent awaken in a state of opioid withdrawal (Gaddis and Watson, 1992; Osterwalder, 1996).

Naloxone-induced withdrawal is also common in out-of-hospital settings in which non-medical persons are asked to administer naloxone to save the lives of their peers. Analysis of the Opioid Lab's overdose reports from the individual who administered NLX found that 98% of overdose victims presented notable opioid withdrawal-related adverse events (AEs) including: nausea, abdominal pain, vomiting, joint/muscle pain, and tremor. Concerns of the adverse effects of NLX administration may prevent or delay the use of this life-saving intervention.

The goal of the proposed, proof-of-concept study is to test the combined effects of vaporized marijuana [Delta-9-tetrahydrcannabinol (THC)] with NLX as a proof of concept towards the possible development of a combined overdose reversal agent with improved tolerability. Marijuana will not actually be vaped per se, but a “vaporizer” will be used to produce an aerosol from marijuana plant material, which the participant will inhale. Marijuana plant material will be obtained from the National Institutes on Drug Abuse (NIDA). In clinical studies, oral synthetic THC (Bisaga et al., 2015; Lofwall et al., 2016) reduced the severity of opioid withdrawal during opioid detoxification (Scavone et al., 2013). Clinically, cannabinoid drugs like Marinol® (oral synthetic THC), Sativex ® (nabixomols), and Cesamet® (nabilone) are used to treat nausea and vomiting, common symptoms of opioid withdrawal. This study will investigate the ability of vaporized marijuana (V-MJ) (0.00, 12.5, and 25 mg; concentration= 11.7% THC + 0.04% CBD.) to reduce the severity of opioid withdrawal precipitated by intranasal (IN) NLX (0.0 and 4.0 mg). The final dose of marijuana will be achieved in 10 puffs/vapes, in 10-12 minutes (at a temperature of 210°C).

This trial will recruit healthy participants with opioid use disorder (N=16, completers).

Testing will begin following stabilization on oral morphine (120 mg/day), which will continue throughout the trial. During each testing session, a single V-MJ + naloxone dose combination will be assessed (in randomized order), with **24 hours** between testing sessions. Laboratory testing sessions will consist of a modified naloxone challenge procedure, which quantifies the severity of naloxone-precipitated opioid withdrawal (Jones et al., 2019).

The slow rate of onset for oral cannabinoid administration would not have utility in an emergency. Therefore, the rapid pharmacodynamics of vaporized marijuana will allow the investigators the opportunity to investigate the potential utility of an ecologically valid combined cannabinoid + NLX opioid overdose emergency intervention. The investigators hypothesize that the combined administration (V-MJ + NLX) will produce significantly less withdrawal than NLX alone.

## **Background, Significance and Rationale**

### Background, Significance and Rationale

Why is naloxone-precipitated withdrawal a problem? Although there are studies that suggest that the distribution of naloxone (NLX) has a measurable effect on overall opioid overdose death rates, deaths nation-wide remain high (Centers for Disease Control (CDC), 2018; Doe-Simkins et al., 2012; Walley et al., 2013). More needs to be done to address the fatalities associated with opioid overdose. All 50 states currently allow medical providers to prescribe the opioid receptor antagonist NLX to persons most likely to witness or experience an opioid overdose. In our study team's investigation into the utility of overdose education and naloxone distribution (OEND) programs, an important barrier has emerged (Jones et al., 2014; Neale et al., 2020). Experienced opioid users have a notable baseline knowledge of opioid overdose and are keenly aware of the ability of NLX to elicit severe opioid withdrawal (Jones et al., 2014; Green et al., 2008). These individuals are also likely to have experienced NLX-precipitated withdrawal during a previous non-fatal overdose (Darke et al., 2014; Mars et al., 2015; Wagner et al., 2015). Additionally, many OEND programs inform individuals that precipitated withdrawal is a likely consequence of administering NLX (Clarke et al., 2014). Thus, the fear of inducing withdrawal is a significant barrier to NLX use, even in emergency situations (Wright et al., 2006). This fear is not unwarranted. In emergency settings, NLX administration often results in violent patient behavior (Gaddis and Watson, 1992; Osterwalder, 1996). Concerns of the adverse effects of NLX administration may prevent or delay the use of this life-saving intervention. Precipitated opioid withdrawal is also a concern for the overdose victim. Once revived, the adverse symptoms such as: joint and muscle pain, nausea, vomiting, and stomach cramps, may lead the individual to use additional opioids for relief, putting them at risk of a recurrence of severe respiratory depression (Buajordet et al., 2004).

How cannabinoids may help? The endocannabinoid system is a potential novel target for reducing opioid withdrawal severity. Studies show that opioid and cannabinoid receptors are co-localized in multiple brain regions. Both receptors also have cross-modulatory pharmacological effects including: cross-agonism, -antagonism, -sensitization, and -tolerance (Robledo et al., 2008). Preclinical studies have demonstrated that tetrahydrocannabinol (THC) decreases signs of opioid withdrawal in morphine-dependent rodents (Bhargava, 1976; Cichewicz and Welch, 2003; Gamage et al., 2015; Hine et al., 1975). In clinical studies, oral dronabinol (synthetic THC: Bisaga et al., 2015; Lofwall et al., 2016) and smoked cannabis have been shown to reduce the severity of abstinence-induced opioid withdrawal during opioid detoxification or

stabilization (Scavone et al., 2013). Clinically, cannabinoid receptor type-1 agonists such as, Marinol® (oral synthetic THC), Sativex® (nabixomols), and Cesamet® (nabilone) are used to treat nausea and vomiting, common symptoms of opioid withdrawal. Joint and muscle pain are also common AEs associated with NLX-precipitated withdrawal. In clinical laboratory investigations of their analgesic effects, cannabinoids have shown promise in treating muscle pain (Cooper et al., 2013 & 2018).

**Rationale:** This study will investigate the ability of vaporized marijuana (V-MJ) (0.00, 12.5, and 25 mg: concentration= 11.7% THC) to reduce the severity of opioid withdrawal precipitated by intranasal (IN) NLX (0.0 and 4.0 mg). If our hypotheses are supported, this study may suggest that the combination of an intranasal opioid receptor antagonist with a cannabinoid receptor agonist may have clinical utility as an overdose reversal medication that is more tolerable than naloxone alone. Reducing the adverse effects of naloxone administration may increase its utilization while minimizing risks for the administrator and recipient.

## **Specific Aims and Hypotheses**

### Specific Aims and Hypotheses

**Primary Aim:** Assess the ability of vaped marijuana to alter the severity of naloxone-precipitated withdrawal. We hypothesize that there will be a dose-dependent effect of vaped marijuana to attenuate the severity of naloxone-precipitated withdrawal.

**Secondary Aim:** Assess the safety of vaped marijuana in combination with naloxone. We hypothesize that vaped marijuana, in combination with naloxone, will produce more AEs than placebo but less than naloxone alone.

**Secondary Aim:** Assess the impact of vaped marijuana on naloxone's effects on pupil diameter (i.e.,  $\mu$ -opioid receptor blockage). We hypothesize that vaped marijuana will not significantly alter naloxone's effects on pupil diameter (in comparison to placebo).

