### Study Assessments:

- Modified Naloxone Challenge
- Systematic Assessment for Treatment Emergent Events (SAFTEE: Levine and Schooler, 1986). Adverse events (AEs) unrelated to withdrawal will be quantified using this scale.
- Pupil diameter will be measured as a proxy of  $\mu$ - opioid receptor activation.
- Drug “Liking”, and other subjective drug effects will be assessed using a Visual Analog Scale (VAS).
- Opioid Craving Questionnaire (adapted from Tiffany and Drobes, 1991; Tiffany et al., 1993).
- Subjective and Clinical Opiate Withdrawal Scales (Handelsman et al., 1987; Wesson and Ling, 2003). Withdrawal Scales (Handelsman et al., 1987; Wesson and Ling, 2003)
- Cognitive Tasks: Two cognitive tasks will be used: The Digit Symbol Substitution Task (DSST; McLeod et al., 1982) assesses psychomotor ability and the Divided Attention Task assesses attention (DAT; Miller, 1987).
- Brief Psychiatric Rating Scale (BPRS: Ventura et al., 1993) used to measure psychiatric symptoms such as anxiety, depression, and psychoses.
- Apple Watch or FitBit for Analysis of Sleep Quality and ECG throughout the testing session.

Please attach copies, unless standard instruments are used

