STATISTICAL ANALYSES

Data Analysis Plan: The distributions of all continuous variables will be checked for normality, and transformations will be employed (if necessary) before applying specific parametric techniques. Before performing specific analyses, we will examine all outcomes for outliers. All statistical comparisons will be two-sided and the critical level for rejection of the null hypothesis will be considered to be a p-value of < 0.05 . Where needed, False Discovery Rate Analysis will be used to adjust critical p values to control for multiple comparisons. Any comparison where homogeneity is violated will not be considered significant. Means, standard deviations, proportions, and 95% confidence intervals will be used to describe all continuous variables.

Dropouts and Missing Data: As this is an inpatient laboratory study within a controlled setting, we expect only minimal intermittent missing data, though we do expect to have some subjects drop out without completing all of the experimental conditions. We will use all available data from subjects prior to drop-out. We will account for missing data directly using mixed-effects models (MEM) (Diggle et al. 2002). MEMs do not require complete measurements to estimate effects and inferences are valid provided that data are “missing at random” (Little & Rubin, 2002). ‘Missing at random’ (i.e. the missing mechanism does not depend on the value of the unobserved outcome) is un-testable in most medical research and in our study as well. One can assume either parametric or semi-parametric models for the missingness that does depend on the unobserved outcome value and do the analysis (Diggle and Kenward 1994, Kenward 1998). Comparison of the inferences from assuming various models for the missingness provides a measure of the validity of the efficacy estimate from the model that assumes missing ‘at random’. One can also compute a local sensitivity index which measures the change in the estimated treatment effect in a neighborhood of the ‘missing at random’ model for missingness (Rotnitzky et al. 1998). We will perform sensitivity analyses based on these two approaches to assess the effect of the assumption of missing ‘at random’ on the inference.

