Randomization: Once a participant is enrolled, a randomization sequence table will be generated by a blinded statistician. The table will determine the order of testing of the various dose combinations of dronabinol (.00, .35, and .70 mg), and naloxone (0.0, 0.2 and 0.4 mg).

Aims, Outcome Measures, and Hypotheses

Primary Aim: Assess the ability of inhaled dronabinol to alter the severity of naloxone-precipitated withdrawal.

- The primary dependent variable (DV) for this aim will be the total opioid withdrawal score from the testing session. Repeated-measures analysis of variance (ANOVA) will be used to assess differences among the various dose conditions.
- We hypothesize that there will be a dose-dependent effect of dronabinol to attenuate the severity of naloxone-precipitated withdrawal.

Secondary Aim: Assess the safety of inhaled dronabinol in combination with naloxone.

- The primary DVs are the SAFTEE (AEs not related to withdrawal) and physiological parameters. Generalized mixed-effects models with participant as a random effect and an autoregressive correlation structure for the within-participant observations will be used to analyze the total number of AEs and their severity.
- We hypothesize that dronabinol, in combination with naloxone, will produce more AEs than placebo but less than naloxone alone.

Secondary Aim: Assess the impact of inhaled dronabinol on naloxone's effects on pupil diameter (i.e., μ -opioid receptor blockage).

- The primary DV will be pre-to-post- medication change in pupil diameter from each testing session. Repeated-measures ANOVA will be used to assess differences among the various dose conditions.
- We hypothesize that dronabinol will not significantly alter naloxone's effects on pupil diameter (in comparison to placebo).

Secondary Aim: Assess the abuse potential of inhaled dronabinol.

- The primary DV will be pre-to-post- medication change in positive subjective drug ratings such as drug "Liking" and "Good Effect."
- We hypothesize that self-reported dronabinol "Liking" will not be significantly greater than placebo.

Power

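### The pupil aim expects no alteration of naloxone's effect but names only a difference test, no deciding contrast and no margin, so preserved blockade cannot be shown as planned

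*Protocol*

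**What the plan says.** - **Hypothesis.** Protocol, Specific Aims and Hypotheses: the expectation is that "vaped marijuana will not significantly alter naloxone's effects on pupil diameter", compared with placebo. The SAP repeats it for inhaled dronabinol.
- **Meaning of the measure.** Protocol, Study Assessments: "Pupil diameter will be measured as a proxy of" mu-opioid receptor activation. The aim itself equates naloxone's pupil effect with receptor blockade.
- **Endpoint and test.** SAP, Aims, Outcome Measures, and Hypotheses: the outcome is "pre-to-post- medication change in pupil diameter from each testing session", and "Repeated-measures ANOVA will be used to assess differences among the various dose conditions".
- **Error rule.** SAP, Data Analysis Plan: "All statistical comparisons will be two-sided", with the rejection level "considered to be a p-value of < 0.05".
- **Estimation text.** SAP, Power: because the study is exploratory, effect sizes are the main outcome for the secondary aims. Interval length is to show precision, and overlap between conditions is to show the degree of difference. A threshold of clinical importance is mentioned without a number. The section closes by calling the study adequately powered to detect differences for every aim.

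Neither document gives a pupil SD, an expected naloxone pupil effect, a pupil power figure, a margin, or the V-MJ comparison that decides the aim.

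**The concern.** The expected result is an absence of effect, while the named test can only reject an absence of effect. Under that pairing, less precise data make the hypothesis easier to call supported.

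The stakes come from the protocol's own rationale. The study is a proof of concept for a combined overdose-reversal agent, and the pupil aim is the only stated aim that asks whether naloxone's receptor action survives the combination. The primary aim cannot answer that. Lower withdrawal scores are the hoped-for result, but weaker antagonism by naloxone would also lower them. A pupil result read as reassuring without adequate precision would therefore also colour the reading of a positive primary result.

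The contrast is a second gap. An ANOVA across all six dose conditions would probably be significant because of naloxone itself, and that says nothing about V-MJ. The informative quantities are the V-MJ comparisons within the naloxone 4 mg sessions and the V-MJ-by-naloxone interaction.

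**Working it through.** **Inputs.** From the documents: n = 16 completers, within-person design, two-sided 0.05. Assumed, because no pupil figures are given: all effects are expressed in SDs of the within-person difference (active V-MJ + naloxone 4 mg minus V-MJ 0 mg + naloxone 4 mg).

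**1. The plan's own figures.** There is no pupil power figure to reproduce. The nearest figures use the same n. Power comes from the noncentral t with 15 df and non-centrality d × √16 = 4d, taking d as the standardized paired difference.
- Liking, d = 0.84: 88.1%, which agrees with the stated 88%.
- Withdrawal score, d = 0.75: 80.1% two-sided, against the stated 90%. One-sided it is 88.8%.
- The 25% margin of error is close to 1.96 × √(0.25/16) = 24.5%, the worst case for a proportion. That would not apply to a continuous pupil change.

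None of these describes how well the trial can exclude a pupil effect.

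**2. Chance of a non-significant result when V-MJ truly changes the pupil response.** For the paired contrast this is 1 minus the power from the formula in step 1. For the F tests I assume sphericity, a linear V-MJ effect (0, d/2, d) present only under naloxone, and a cell error variance of 0.5, so that a paired difference has SD 1. The non-centrality is 16 × (d²/2)/0.5 = 16d² for the three V-MJ levels under naloxone, and 16 × (d²/4)/0.5 = 8d² for the interaction, each on 2 and 30 df.

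| True effect (SD of paired difference) | One paired contrast | Three V-MJ levels under naloxone | V-MJ-by-naloxone interaction |
|---|---|---|---|
| 0.3 | 80% | 84% | 90% |
| 0.5 | 54% | 62% | 79% |
| 0.75 | 20% | 27% | 58% |

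**3. Precision.** The 95% half-width for a paired contrast is 2.131/√16 = 0.533 SD.

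**4. What a margin-based rule could deliver.** For a fixed margin m on one paired contrast, one-sided 0.025, no true effect, power is P(T > 2.131) with non-centrality 4m:
- m = 0.5 SD: 46% (34 completers would be needed for 80%)
- m = 0.75 SD: 80%
- m = 1.0 SD: 96%

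If the 95% interval must lie inside ±m in both directions, simulated power is 8.5% at 0.5 SD and 60% at 0.75 SD.

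For a rule requiring at least half of naloxone's effect to be retained, suppose naloxone's effect is E at every V-MJ level, with SD 1 per person and no correlation across levels. The contrast is (effect with V-MJ) − 0.5 × (effect without). It has mean 0.5E, SD √(1 + 0.25) = 1.118, and non-centrality 4 × 0.5E/1.118. Power is 39% at E = 1, 71% at E = 1.5 and 92% at E = 2. The documents do not give E.

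**The case against.** The strongest reply is that the SAP does not rest this aim on a p-value. Its Power section puts effect sizes and intervals first for secondary aims, and the study describes itself as exploratory and proof of concept. This stands in part. A reader might infer from the hypothesis wording that any non-significant ANOVA would be declared proof of no interference, but neither document states that rule. What the estimation text lacks is a value for its threshold, a rule linking the interval to a conclusion, and an interval for the right quantity. Overlap of separate per-condition intervals ignores the pairing, and overlapping intervals are not evidence that an effect is preserved.

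A reader might also infer that a falsely reassuring result is likely. The documents do not support this either. With n = 16, a non-significant paired contrast has a 95% interval reaching at most 2 × 0.533 = 1.07 observed SDs from zero. If naloxone's own pupil effect exceeded about 2 × 1.07 = 2.1 of those SDs, every non-significant result would exclude loss of half that effect, ignoring uncertainty in naloxone's effect itself. If it were about 1 SD, many would not. Without a pupil SD or a naloxone effect, nobody can say whether 0.3 or 0.5 SD is trivial or serious.

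**Conclusion.** The concern holds as a gap in specification. The pupil aim states an expectation of no alteration, names only a difference test, leaves the deciding contrast open and sets no margin. The estimation text reduces the problem without closing it. As written, the plan allows preserved blockade to be supported by imprecise data, and its general statement about power concerns detecting differences, not excluding a loss.

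At n = 16 a single paired contrast misses a true 0.5 SD change about half the time (54%) and cannot usually bound the effect more tightly than about ±0.53 SD. These figures assume all 16 complete, roughly normal paired differences, and SD units chosen for want of pupil data. They do not establish that a clinically important loss of blockade would be missed. I also assume that the SAP's pupil analysis, written for dronabinol and for naloxone doses that differ from the protocol's, carries over to V-MJ; the two documents must be reconciled on this.

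**What to change.** In the SAP, for the pupil aim:

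1. Name the contrasts: each active V-MJ dose with naloxone 4 mg against V-MJ 0 mg with naloxone 4 mg, and the V-MJ-by-naloxone interaction. State which decides the aim. The first would mix in any pupil effect of V-MJ itself; the interaction separates it but is less precise.
2. Report each with a within-person 95% confidence interval, replacing the comparison of per-condition intervals by overlap.
3. Before unblinding, set and justify a margin, in mm or as a fraction of naloxone's own pupil effect. State whether one or both directions count. For a fraction, state the interval method.
4. Claim that naloxone's effect is not altered only if the interval clears the margin, and at both active doses if the claim covers both. Otherwise report the aim as estimation only or inconclusive.
5. Remove this aim from the Power section's statement that the study is adequately powered.

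The cost is SAP text and one justified number. All six dose conditions are already in the protocol, so no new sessions or measurements are needed. The downside is that the reassuring conclusion becomes harder to reach: power is about 46% for a fixed 0.5 SD margin and 80% for 0.75 SD, and for a retained-fraction rule it depends on a naloxone effect that the documents do not give.
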